### 13.2.3 Participant restrictions

Items participants must not consume or do	When participants must stop	When participants can re-start
Tobacco in any form (e.g., smoking or chewing) or other nicotine-containing products in any form (e.g., gum, patch, electronic cigarettes)	Any time at the facility during trial participation	When not in the facility
Meals/snacks/water	See Section 6	See Section 6
Not consume any other substances known to be potent inhibitors or inducers of the CYP3A4 system. This includes food or drink products containing cranberry, pomegranate, star fruit, grapefruit, pomelos, exotic citrus fruits or Seville oranges (including marmalade and juices made from these fruits)	Within 30 days or five half-lives (whichever is longer) before the planned first trial drug administration.	After trial completion/last visit.
Caffeine-containing or Xanthine-containing products	48 hours before the planned first trial drug administration and each out-patient/ follow-up visit.	After trial completion/last visit.
Energy drinks or drinks containing taurine, glucuronolactone (e.g. Red Bull)	48 hours before the planned first trial drug administration and each out-patient/ follow-up visit.	After trial completion/last visit.
Alcohol	48 hours before the planned first trial drug administration and each out-patient/ follow-up visit. On other days: less than 14 units a week and less than three units in one day is permitted.	After trial completion/last visit.
Strenuous physical activity	48 hours before screening, admission and out-patient/follow-up visit.	After trial completion/last visit.
Activity	Participants will be requested to remain in a semi-supine position for the first four hours after dosing each day, except to use the bathroom.	

Items participants must not consume or do	When participants must stop	When participants can re-start
	Participants may then be ambulatory but should not engage in strenuous activities and should rest semi-supine for at least five minutes prior to any vital signs or at least ten minutes prior to ECG measurement.	
Any prescription medication	14 days or five half-lives (whichever is longer) before the planned first trial drug administration.	After trial completion/last visit. If participants have a medical need to take any medication or have any medications prescribed to them by a doctor, they should follow the medical advice but inform the Investigator as soon as possible afterwards. Participants should be informed not to stop taking any medication that has been prescribed by their general practitioner or other doctor.
Any over-the-counter medication	Seven days or five half-lives (whichever is longer) before the planned first trial drug administration.	
Any herbal remedy or dietary supplement containing St John's Wort	30 days before the planned first trial drug administration.	After trial completion/last visit.
Blood and plasma donation	90 days before the planned first trial drug administration.	Three months after trial completion/last visit.
Contraception: Participants must comply with the appropriate contraceptive requirements	As indicated in Section 13.2.2	As indicated in Section 13.2.2
COVID-19 vaccination	Four weeks before the planned first trial drug administration	Seven days after trial completion/last visit.

### 13.3 Monitoring

To ensure compliance with the protocol, monitoring visits by a professional representative of the sponsor will be scheduled to take place regularly, and at appropriate intervals according to the monitoring plan.

Monitoring will be conducted according to ICH-GCP. The individuals responsible for monitoring the study will have access to all records necessary to ensure the integrity/validity of the recorded data and will periodically review the progress of the study. The monitor must contact the site prior to the start of the study to discuss the protocol and data collection procedures with the site personnel.

The investigator must agree to allow the monitor direct access to all relevant documents and to allocate his/her time and the time of his/her staff to the monitor to discuss findings and any relevant issues.

Additional site visits may be made during the course of the trial and at the end of the surveillance period as delineated in a monitoring plan approved by IHI and the Sponsor.

The monitoring plan will include the percentage of participant charts to be reviewed, which and what proportion of data fields will be monitored, as well as who will be responsible for conducting the monitoring visits and who will be responsible for ensuring that monitoring findings are addressed. Additionally, the sponsor will perform a Site Qualification visit to assess the suitability of the site for conducting the trial. The trial will only begin following a written approval from the sponsor.

#### **13.4 Audits and inspections**

For the purpose of compliance with ICH-GCP and regulatory guidelines, it may be possible that the sponsor/designee or a national ethics or regulatory authority may conduct a site audit/inspection. This may occur at any time from start to conclusion of the study.

The QA designated site staff will conduct internal audits to check that the trial is being conducted, data recorded, analyzed and accurately reported according to the protocol, sponsor's SOPs and in compliance with ICH GCP. The audits will also include laboratory activities according to an agreed audit schedule.

The investigator agrees to allow the auditor direct access to all relevant documents and to allocate his/her time and the time of his/her staff to the auditor to discuss findings and any relevant issues.

If a regulatory authority requests an inspection, the investigator must inform the sponsor or its designee immediately about this request. The investigator(s) and the study coordinator(s) must make the relevant records available for inspection and must be available to respond to reasonable requests and audit queries made by authorized representatives of regulatory agencies. The sponsor will provide any needed assistance in responding to regulatory audits or correspondence.

#### **13.5 Confidentiality, data protection**

The study will be monitored by the CRO subcontracted by the sponsor. CRO representatives and representatives of the local Regulatory Authorities and Ethics Committees will be allowed access to all information resulting from this study including the access to study-related documentation. The subjects' confidentiality will be respected as required by local law.

All parties agree to adhere to the principles of medical confidentiality in relation to Clinical Study Subjects involved in the Clinical Study. Neither party shall disclose the identity of Clinical Study Subjects to third parties without prior written consent of the Clinical Study Subject.

The trial staff will ensure that the participants' anonymity is maintained. The participants will be identified only by a participant study ID on all trial documents, study participant card, and any electronic database. All documents will be stored securely and only accessible by trial staff and authorized personnel only.

The trial will comply with the Data Protection Act, 1998, which requires data to be anonymized as soon as it is practical to do so.

#### **13.6 Storage of biological material and related health data**

The data and remaining biological materials related to the trial will be stored at the IHI archive and laboratories in Bagamoyo. All study data will be archived for a minimum of 25 years after study termination or premature termination of the clinical trial. The samples will be destroyed after the specified period. Participants will be asked for their consent to allow institutional ethics review boards to use anonymized data and aliquots of the samples for assessments of other markers of infectious disease or protection.

### **13.7 Safety Review Committee (SRC)**

A formal Safety Review Committee (SRC) will be established by the sponsor to oversee the study.

The SRC will evaluate the data at the interim analysis and provide recommendations to the Sponsor with regard to continuation of the study (more details are provided in the SRC charter).

The SRC's composition, responsibilities and procedures will be pre-specified in details by a safety monitoring charter. The members of the SRC are responsible for decisions related to the safety of participants and the continuation of the study. The SRC will assess all preliminary safety and available PK data whenever indicated as a result of safety concerns. They will decide on the appropriateness of subsequent cohorts and the continuation of the study.

At the minimum, the SRC will include the following members (more details are provided in the SRC charter):

- the principal investigator or delegate
- the medical monitor or delegate
- the medical director or delegate
- the independent local safety monitor

## 14 FUNDING

The study will be funded by the sponsor (Medicines for Malaria Venture (MMV)). The Sponsor, the Principal Investigator and supporting organizations / institutions declare to have no conflict of interest.

The Investigators, including the Principal Investigator and/or any sub-Investigators, directly involved in the treatment or evaluation of participants may be requested to provide a financial disclosure. All relevant documentation will be filed in the Trial Master File.

## 15 DISSEMINATION OF RESULTS AND PUBLICATION POLICY

### **15.1 Dissemination to scientific community; incl. lead in publications**

All data and results generated in the study will be owned by the Sponsor, who may utilize them in various ways, such as for submission to the regulatory authorities.

The Sponsor will make the results derived from the study freely publicly available through appropriate open access databases, repositories and similar tools. The Sponsor will not specifically protect them as intellectual property, i.e. not to file any patent application, or otherwise protect, assert or take any action to enforce any rights on such results.

The Investigators will be involved in writing and/or reviewing drafts of the manuscripts, abstracts, press releases and any other publications arising from the study. Apart from obvious flaws to the conduct of the study, which may preclude data publication, safety and efficacy data will be published under the supervision, review and formal authorization of the Sponsor.

Authorship follows the International Committee of Medical Journal Editors (ICMJE) principles, publications will follow CONSORT statement.

Authorship for publication in scientific journals will be offered to each party that has substantially contributed to the work reported in the publication. It is expected that authorship of such publications will be led by the Sponsor.

The final clinical study report will be the responsibility of the Sponsor and will be submitted to the regulatory authorities and ethics committee(s), if required by these bodies when available.

The Sponsor encourages the communication and/or publication of the results, in accordance with the terms of the Clinical Trial Agreement.

### **15.2 Information of community and policy makers**

Study outcomes will be disseminated to study communities and local authorities at the end of the study. A final safety report will be submitted to all ethics committees and regulatory authorities.

SD	Standard Deviation
SEM	Standard Error of Mean

SOC	System Organ Class
TEAEs	Treatment-Emergent Adverse Events
TLFs	Tables, data listings, and figures
T_{max}	Time at which the maximum plasma concentration occurs
$t_{1/2}$	Terminal elimination half-life
WHO	World Health Organization
WHO-DD	WHO Drug Dictionary
ENRL	Enrolled Population Set
SAF	Safety Analysis Set
PK	PK Analysis Set
PQP	Piperaquine phosphate
LOQ	Limit of Quantification
Vz/F	Apparent volume of distribution during the terminal phase
λ_z	Terminal rate constant

1. Overview**1.1 Introduction**

The purpose of this Statistical Analysis Plan (SAP) is to provide details of the statistical analyses that have been outlined within Protocol MMV_SMC_22_01 version 3.0 dated 08 Nov 2023. The scope of this plan includes the final analysis, which will be executed by the Biostatistics department unless otherwise specified.

The present pilot BA/FE study aims to assess the relative bioavailability and food effect on the systemic exposure of a new child-friendly, taste-masked dispersible granule formulation of PQP among healthy adults. In addition, PK and safety/tolerability profiles will be further evaluated and documented.

2. Trial objectives

The following objectives are those stated in the protocol.

2.1 Primary objective

- To determine the relative bioavailability of a single oral dose of PQP dispersible granule formulation (Test) as compared to PQP hard tablet formulation (Reference) in the fasted state.

2.2 Secondary objectives

- To assess the effect of different types of meal composition on the PK of single doses of PQP dispersible granule formulation in healthy adult participants.
- To further evaluate the PK of a single oral dose of PQP granule formulation in the fasted state and different fed states in healthy adult participants.
- To further document the safety/tolerability of PQP in healthy adult participants.

2.3 Exploratory objectives

- To further document PQP metabolite profiling and PK depending on the results of a former study (optional objective) as well as the results of genetic testing of CYP450s polymorphism (optional).
- To evaluate the palatability of the new PQP granule formulation in healthy adult participants.

3. Endpoints

3.1 Primary endpoint

- Relative bioavailability (F_{rel}) using the ratio of the geometric means for the dispersible granule (test) over the hard tablet (reference) in a fasted state for the area under the plasma concentration-time curve from time zero to 72 hours (AUC_{0-72h}), area under the plasma concentration-time curve from time zero to last detectable plasma concentration (AUC_{0-t}), area under the plasma concentration-time curve from time zero to 168 hours (AUC_{0-168h}), area under the plasma concentration-time curve from time zero extrapolated to infinity ($AUC_{0-\infty}$), and maximum plasma concentration (C_{max}).

3.2 Secondary endpoints

- PK parameters for the hard tablet (fasted) and the dispersible granule formulations (fasted and fed); C_{max} , AUC_{0-24h} , AUC_{0-72h} , AUC_{0-t} , AUC_{0-168h} , $AUC_{0-\infty}$, time to maximum plasma concentration T_{max} , terminal elimination rate constant (λ_z), terminal elimination half-life ($t_{1/2}$), apparent volume of distribution during the terminal phase (V_z/F), apparent total plasma clearance (Cl/F), and percentage of AUC that is due to extrapolation from t_{last} to infinity ($\%AUC_{extrap}$).
- Occurrence of AEs including serious adverse events (SAEs) from the IMP administration throughout the entire study period (up to Day 30).
- Findings at different time points:
 - Physical examination, vital signs, clinical laboratory safety parameters, 12-lead ECG parameters.

4. Trial design

4.1 Design overview

This is a randomized, open-label, parallel-design study to evaluate the PK profile and relative bioavailability of a single dose of a PQP oral granule formulation dispersed in water (test) as compared to the PQP hard tablet formulation (reference) in fasting conditions (Part 1) and to assess the BA/FE of the PQP dispersible granules formulation when administered with different food restrictions (Part 2) among African participants residing in Tanzania, in Bagamoyo Town and surrounding areas. A total of sixty (60) healthy adult participants (male and female) will be enrolled in Part 1 and Part 2.

- **Part 1:** PQP tablet / dispersible granule administered in fasting condition of at least 10 hours.
 - Group 1: PQP hard tablet, 320 mg (N=12)
 - Group 2: PQP dispersible granule, 320 mg (N=12)
- **Transition to Part 2:**
 - To minimize the risk to healthy participants, a decision on transitioning from Part 1 to Part 2, will be taken by the Safety Review Committee (SRC) see protocol section 13.7, based on the safety and preliminary PK interim report of the granule formulation, compared to the PQP hard tablet, with safety data obtained up to Day 15 and PK data obtained up to Day 8. If necessary, doses may be readjusted for Part 2 to assess the food effect. A description of the rationale and oversight related to the potential for dose adjustment is provided in protocol section 2.2.
- **Part 2:** PQP dispersible granule administered in fed conditions (planned as 320 mg)
 - Group 3: High-fat meal (N=12)
 - Group 4: Low-fat meal representative of African diet (N=12)
 - Group 5: Whole milk 250 ml (N=12)

Participants will be screened within a window of ≤ 45 days before in-house admission on Day -1. Each participant will be admitted to the trial unit on Day -1, and after a new eligibility check, will receive a single dose of PQP on Day 1 and will be discharged on Day 3 (a total of 4 in-house days). Participants will attend the trial unit clinic for outpatient visits on Days 8, 15, 22, and 30.

4.2 Randomization

Healthy adult participants (male and female) will be randomly allocated to one of the 5 following treatment groups, dosing will be carried out in the fasted or fed state:

- During the study part 1, participants for fasted conditions will be randomly allocated to either group 1 (n=12) or group 2 (n=12), in order to assess the relative bioavailability of the dispersible granules formulation as compared to the hard tablet formulation.
 - Randomization will occur in blocks of 2 (each block contains 1 assignment from each of the groups 1 and 2).
- During study part 2, participants for fed conditions will be randomly allocated to either group 3 (n=12), 4 (n=12), or 5 (n=12), in order to assess the food effect after dosing of PQP dispersible granules formulation.

- Randomization will occur in blocks of 3 (each block contains 1 assignment from each of the groups 3, 4, and 5).

A computer-generated randomization schedule will be used and will be accessible only to the site-delegated study staff who will prepare the treatment for each participant according to the randomization allocation.

4.3 Determination of sample size

This is an exploratory trial to evaluate the PK and safety of each treatment group and the sample size is not based on formal statistical power. The number assigned to each treatment arm (n=12) is considered adequate to assess the trial objectives.

4.4 Schedule of Events

Refer to section 4.4 schedule of events of the protocol.

5. Changes/deviations from the planned analysis

The statistical analysis/methods as described in the protocol were adopted. There are no changes to the planned analyses. Any deviation from the original statistical analysis plan will be described and justified in the SAP or final clinical study report.

6. Analysis of populations

Protocol deviations will be reviewed, and exclusion of participants from each analysis sets will be decided during data review meeting prior to the final database hard lock. A list of all participants to be excluded from the relevant analysis populations, including the reason(s) for exclusion from the analysis populations will be provided.

The following sets will be used for the statistical analyses:

6.1 Enrolled Analysis Set (ENRL)

This population will include all participants who signed the informed consent form (ICF).

6.2 Safety Analysis Set (SAF)

This population will include all randomized participants who received at least one dose of the IMP.

6.3 PK Analysis Set (PK)

The PK analysis set will include those participants in the safety set who have sufficient blood samples taken for at least one of the PK variables to be calculated and experienced no protocol deviations with relevant impact on PK data.

7. General considerations

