## 4 STUDY DESIGN

This is a randomized, open label, parallel-design study to evaluate the PK profile and relative bioavailability of single dose of a PQP oral granule formulation dispersed in water (test) as compared to the PQP hard tablet formulation (reference) in fasting conditions (Part 1) and to assess the BA/FE of the PQP dispersible granules formulation when administered with different food restrictions (Part 2) among African participants residing in Tanzania, in Bagamoyo Town and surrounding areas. A total of sixty (60) healthy adult participants (male and female) will be enrolled in Part 1 and Part 2.

- **Part 1:** PQP tablet / dispersible granule administered in **fasting condition** of at least 10 hours
  - Group 1: PQP hard tablet, 320 mg (N=12)
  - Group 2: PQP dispersible granule, 320 mg (N=12)
- **Transition to Part 2:**
  - To minimize the risk to healthy participants, a decision on transitioning from Part 1 to Part 2, will be taken by the Safety Review Committee (SRC) see Section 13.7, based on the safety and preliminary PK interim report of the granule formulation, compared to the PQP hard tablet, with safety data obtained up to Day 15 and PK data obtained up to Day 8. If necessary, doses may be readjusted for the Part 2 in order to assess the food effect. Description for the rationale and oversight related to the potential for dose adjustment is provided in Section 2.2.
- **Part 2:** PQP dispersible granule administered in **fed conditions (planned as 320 mg)**
  - Group 3: High-fat meal (N=12)
  - Group 4: Low-fat meal representative of African diet (N=12)
  - Group 5: Whole milk 250 ml (N=12)

In summary: Participants will be screened within a window of  $\leq$  45 days prior to in-house admission on Day -1. Each participant will be admitted to the trial unit on Day -1, and after a new eligibility check, will receive a single dose of PQP on Day 1 and will be discharged on Day 3 (a total 4 in-house days). Participants will attend the trial unit clinic for outpatient visits on Days 8, 15, 22 and 30. Details of procedures and parameters to be assessed at each study time points are outlined in Section 7 (Study Assessments and Visits) and summarized in Section 4.4 (Schedule of events).

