### 4.2.2 Blinding

The trial will be open-label i.e., participant, investigator and sponsor will be unblinded to treatment and meal conditions assignation. Therefore, after treatment allocation by the site pharmacist according to the randomisation schedule, the study investigators will be provided with the explicit details related to the treatment (Part 1) or feeding conditions (Part 2).

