### 10.5 Analysis sets

The analysis of data will be based on different analysis sets according to the purpose of analyses. Participant eligibility for each analysis set will be finalised before the database hard lock.

The Safety analysis set will consist of all randomized participants who received at least one dose of the IMP.

The PK analysis set will consist of those participants in the safety set who have sufficient blood samples taken for at least one of the PK variables to be calculated.

In all populations, analyses will be based on the treatment received, regardless of the randomization (any such deviations will be reported). A participant who withdraws prior to the last planned observation in a trial period will be included in the analyses up to the time of discontinuation.

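### The SAP adds a deviation exclusion to the PK set without declaring it, and no planned output shows how exclusions change the primary and food-effect ratios

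*SAP*

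**What the plan says.** **Definition of the PK set.** Protocol 10.5 takes members of the safety set "who have sufficient blood samples taken for at least one of the PK variables to be calculated". It has no deviation criterion; the synopsis agrees. SAP 6.3 keeps this condition and adds that the participant must have "experienced no protocol deviations with relevant impact on PK data". Neither document says which deviations count. SAP 10.2 grades deviations as major or minor but does not tie the grade to set membership.

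**Declared changes.** SAP Section 5 states: "There are no changes to the planned analyses".

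**How exclusions are decided.** SAP Section 6 states: "exclusion of participants from each analysis sets will be decided during data review meeting prior to the final database hard lock". Attendees are not named, and nothing is said about which data they see.

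**Who knows what.** Protocol 4.2.2 states that "participant, investigator and sponsor will be unblinded to treatment and meal conditions assignation". Under protocol Section 4, the Safety Review Committee (SRC) decides on moving to Part 2 from an interim report comparing granule with tablet, "with safety data obtained up to Day 15 and PK data obtained up to Day 8". Protocol 13.7 lists the principal investigator and "the medical director or delegate" among its members.

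**What is reported.** SAP 18.1.2 and 19.1.2 run the ratios on the PK set only. Listing 16.2.5.4 gives PK parameters for the PK set only. Exclusions and their reasons are summarised and listed (SAP 6, SAP 10.2, Listing 16.2.3.1).

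**The concern.** The set on which the primary endpoint is estimated differs between protocol and SAP, and the SAP section meant to record such differences says there are none. The added condition is a judgement, taken when allocation is open and when some trial roles have seen part of the Part 1 PK data. Piperaquine concentrations are objective measurements, but who contributes them to the ratio is not. With 12 participants per arm, one membership decision can change the estimate noticeably.

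The reach goes beyond the primary endpoint. Group 2 (granules, fasted) is the test arm in Part 1 and the only reference for the three fed comparisons in Part 2. One Group 2 exclusion therefore enters four ratios on each of five parameters. It moves the primary ratio one way and the three food-effect ratios the other. Protocol 3.1.1 says the study will inform dose selection of the granule formulation, so these ratios will be used even though the trial is a pilot.

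**Working it through.** **Plan's own figures.** The documents give no variability, power or margin, so there is no such figure to reproduce. The participant count agrees: 5 × 12 = 60 = 24 + 36.

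**Inputs.** n = 12 per arm (protocol Section 4). The estimate is a ratio of geometric least squares means with treatment as the only fixed effect (SAP 18.1.2), so each arm's value is its plain log-scale mean. The 90% CI is also from SAP 18.1.2. Exposure is assumed log-normal with between-subject CV from 30% to 80%; these CVs are assumptions.

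**Formulas.**
- Log-scale SD: s = √ln(1 + CV²).
- Worst case, one arm: the expected extreme of 12 standard normal values is 1.629 from the mean. The 12 deviations sum to zero in expectation, so the other 11 average 1.629/11 = 0.148 the other way. Shift factor = exp(0.148 s).
- Worst case, one extreme participant dropped in each arm in opposite directions: the square of that factor.
- Exclusion unrelated to outcome, typical (1 SD) shift: exp(s·√(1/11 − 1/12)) = exp(0.0870 s).
- 90% CI half-width factor, 12 v 12: exp(1.717 · s · √(1/12 + 1/12)) = exp(0.701 s).

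| Assumed CV | s | Worst case, one arm | Worst case, both arms | Unrelated to outcome | 90% CI factor |
|---|---|---|---|---|---|
| 30% | 0.294 | 1.04 | 1.09 | 1.03 | 1.23 |
| 50% | 0.472 | 1.07 | 1.15 | 1.04 | 1.39 |
| 70% | 0.632 | 1.10 | 1.21 | 1.06 | 1.56 |
| 80% | 0.703 | 1.11 | 1.23 | 1.06 | 1.64 |

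**Group 2 example.** At 50% CV, dropping the lowest Group 2 participant multiplies the granule/tablet ratio by 1.07 and each fed/fasted ratio by 1/1.07 = 0.93.

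**What the interim report could reveal.** With Day 1 as time zero, Day 8 is 7 × 24 = 168 h. PK data to that point could cover Cmax, AUC0-72h and AUC0-168h, three of the five primary parameters. AUC0-t and AUC0-∞ would not be final.

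**What a reader could recover.** Listing 16.2.5.3 gives concentrations for the enrolled population, so an excluded participant's concentrations should remain visible. That participant's AUC and Cmax need not appear. To see the effect of an exclusion, a reader would have to repeat the non-compartmental analysis.

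**The case against.** Leaving out participants whose deviations compromise their PK data is routine, and the exclusions with reasons will be on record. Fixing the sets before hard lock is also in protocol 10.5, so the timing is no departure. The protocol tests no hypothesis, neither document states an acceptance margin that a shift could cross, and every one-arm shift above lies well inside the CI factor. Details of the PK analysis are assigned to a separate PK analysis plan (protocol 10.7), which may contain exclusion rules. All of this stands and limits the weight of the point.

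Several stronger readings are tempting but not supported:
- *Exclusions will be decided with Part 1 concentrations in view.* The interim report goes to the SRC. No text says who attends the data review or that PK results are tabled there. What can be said is that nothing prevents it.
- *An unfinished meal or a late sample could be used to move the primary ratio.* The primary comparison is fasted, so an incomplete test meal can affect only the Part 2 ratios. Protocol 10.7 derives parameters from actual sampling times, which largely handles late samples. A concomitant drug is a more relevant example.
- *Exclusions would be hidden.* They would be listed with reasons; what is missing is their effect on the ratios.
- *This is the main route by which open allocation could act.* Protocol 6.6 already leaves replacement after vomiting to the investigator and sponsor.
- *A shift of 4% to 11% should be expected.* That requires the excluded person to be the most extreme of 12, and the CVs are assumed.

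What remains is the mismatch in definition, the inaccurate statement in SAP Section 5, and the lack of any analysis on the protocol-defined set.

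**Conclusion.** The point holds as a cheap improvement. SAP 6.3 changes the primary analysis population relative to protocol 10.5, and SAP Section 5 does not say so. The change rests on an undefined judgement with no stated barrier to seeing concentrations, and its effect on the primary and food-effect ratios would not be reported. One exclusion could shift a ratio by about 4% to 11% in the worst case (CV 30% to 80%), or typically by about 3% to 6% if unrelated to outcome (CV 30% to 70%). These sizes rest on log-normal exposure and assumed CVs. The documents show that exclusions could move the ratio, not that any has.

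**What to change.** 1. **SAP 18.1.2 and 19.1.2:** report the ratios on the protocol 10.5 PK set beside those on the SAP 6.3 set.
2. **SAP Section 5:** declare the changed PK-set definition.
3. **SAP Section 6:** decide PK-set exclusions from a deviation listing that carries no concentrations or PK parameters, and sign the list before it is merged with the PK data. Full masking of group is not realistic: the trial is open label, deviation text can reveal the group, and some reviewers may already know interim Part 1 results.

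Cost: SAP wording, one restricted listing, and a repeat of Tables 14.2.1.3 and 14.2.1.4. The downside is two sets of ratios to present. No new data are needed. If concentrations have already been seen, items 1 and 2 remain possible and useful.
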